9.1. Demographics and Other Baseline Characteristics

9.1.1. Informed Consent

The nature of the study and its risks and benefits will be explained to the subject by the Investigator or designated study personnel. The subject must voluntarily provide written informed consent on an ethics-approved informed consent form (ICF), prior to performing any study-related procedures. The subject's medical records must document that the consent process has been completed and that written informed consent has been obtained from the subject prior to the initiation of any study-specific procedures. Documentation that the subject was given adequate time to ask the Investigator (or designee) questions about their participation in the study and that a signed and dated copy of the ICF was provided to the subject should also be included in the medical records or clinical chart.

9.1.2. Demographics

The following demographics will be recorded: age (birthdate), sex, race, and ethnicity. A complete psychosocial history will be obtained including education, employment status, marital/significant other status, residential status and legal status/arrest history.

9.1.3. Medical History

The complete medical history based on patient interview of 5 years prior to the screening visit and any clinically significant medical history greater than 5 years prior to the screening visit will be collected, these will include histories of acute, chronic, or infectious disease; surgical or oncologic histories; and any reported conditions affecting major body systems. All findings on medical history will be evaluated by the Investigator for clinical significance.

9.1.4. Medication History

All medications (prescription and non-prescription, herbal medications/natural health products, or investigational drugs) taken by the subjects during the 30 days prior to Screening will be recorded in the source documentation as medication history. Substance Abuse History and Treatments will be collected separately.

9.1.5. Substance Use and Treatment History

A complete history of previous and current illicit drug use, substance abuse/dependence, and treatments for any substance use disorders (pharmacologic as well as non-pharmacologic) will be obtained. This will include drugs used, type, frequency and patterns of abuse, routes, doses, drug preferences and concomitant medications, using questionnaires. Detailed information on substance use and treatment history is provided in the Study MOP.

9.1.6. Contraceptive Requirements

Women of childbearing potential must agree to use highly-effective method(s) of birth control as defined in the informed consent form and must agree to be tested for pregnancy.

Highly-effective method(s) of birth control include:

- Established use of progestogen-only oral, injectable or implantable hormonal methods of contraception (for example contraceptive pills, implants, transdermal patches, hormonal vaginal devices or injections with prolonged release).
- Established use of combined estrogen and progestogen oral, intravaginal or transdermal hormonal methods of contraception (for example contraceptive pills, implants, transdermal patches, hormonal vaginal devices or injections with prolonged release).
- Placement of an intrauterine device (IUD)
- Intrauterine hormone-releasing system (IUS).
- Vasectomized male partner (with the appropriate post-vasectomy documentation of the absence of sperm in the ejaculate and provided this partner is the sole sexual partner of the female study participant of childbearing potential).

Male subjects must agree to use condoms throughout the course of the study (from Screening to Follow-up).

Women of childbearing potential must have a confirmed negative pregnancy test at study entry. They must use an effective contraceptive method throughout the entire duration of the study treatment, and agree to repeat urine pregnancy test at designated visits. The applied methods of contraception have to meet the above criteria for a highly effective method of birth control.

Sterilized or infertile subjects are exempt from the requirement to use contraception. In order to be considered sterilized or infertile, subjects must have undergone surgical sterilization (vasectomy/bilateral tubectomy, hysterectomy and bilateral ovariectomy, as determined by subject medical history) or congenially sterile, or must be post-menopausal. Postmenopausal women must be amenorrheic for at least 12 months.

9.2. Eligibility Review

Prior to receiving CAM2038 on Day 1, subjects must meet all inclusion and not meet any exclusion criteria as outlined in Section 7.4 and 7.5.

The Investigator or Sub-Investigator must document that the subjects meet each individual criterion via a signed note or eligibility and clinical stability checklist during Screening. Signatures on these documents must be dated on or before the date of Day 1.

9.3. Efficacy Assessments

Details regarding exploratory efficacy endpoints are provided in Section 9.6 (Efficacy Variables). The following sections provide an overview of the efficacy assessments included in the study. Additional details, such as the questionnaire items/scale text and additional instructions (where applicable) are provided in the Study MOP.

9.3.1. Urine Toxicology for Opioids

Urine toxicology samples will be collected at each visit using a urine collection cup containing a temperature sensor. Specimen authenticity will be verified at the site using this sensor to measure

the urine temperature immediately following collection. The temperature of a urine sample within 4 minutes of voiding should fall within the range of 32.2 to 37.7 degrees Celsius (90 to 100 degrees Fahrenheit). If test results are outside these ranges, the subject will be asked to immediately provide another urine sample. If this second sample is outside of the temperature range, the sample will be counted as 'missing', and should not be sent for analysis (any such samples must be documented in the subject's records). A direct observation approach to obtaining urine samples may be used if the Investigator deems it necessary (in Sweden and France, supervision of urine sampling is mandatory). Urine samples will be logged and numbered and then sent to a central laboratory for analysis for the presence of opioids (e.g., morphine and metabolites, oxycodone, hydrocodone, hydromorphone, fentanyl, and methadone). In addition, it is recommended that the scheduled assessment visits take place on Mondays to potentially improve detection of illicit opioid use that may have occurred over the weekend.

9.3.2. Self-Reported Illicit Drug Use

Subjects will be questioned about illicit drug use, including illicit or prescription opioids and other drugs of abuse using a timeline follow-back type of interview (Fals-Stewart et al, 2000). A copy of the Illicit Drug Use Self-Report form is provided in the Study MOP.

9.3.3. Measures of Desire and Need to Use

Desire to Use and Need to Use will be administered using unipolar 100 mm VAS ("Since your last scheduled assessment visit, indicate your worst or strongest desire/need to use opioids, where 0 = No desire to use and 100 mm= Strongest possible desire, and from 0=No need to use and 100 mm=Strongest possible need, respectively) outcome (Kozlowski et al, 1989).

Copies of these VASs are provided in the Study MOP. ***NOTE: Only VAS copies provided by the Sponsor should be used with study subjects; photocopies made locally may result in changes to the length of the scale, leading to inaccurate results.***

A separate VAS will be provided for each Desire to Use and Need to Use and measurements must be taken separately (i.e., separated in time or by other procedures).

9.3.4. Quality of Life Questionnaires and Patient Satisfaction Scale

Two quality of life questionnaires will be provided to subjects for completion:

- Work Productivity and Activity Impairment Questionnaire-General Health (WPAI-GH) (Reilly Associates).
- EQ-5D-5L Health Questionnaire (EuroQOL Group Association).

These are to be completed on a monthly basis, approximately every four weeks at the subjects scheduled visit.

A patient satisfaction scale will be provided to subjects for completion at month 6 and month 12 (EOT).

Copies of the WPAI-GH, EQ-5D-5L and patient satisfaction scale is provided in the Study MOP.

9.3.5. Measures of Withdrawal

9.3.5.1. Subjective Opioid Withdrawal Scale (SOWS)

Subjects will complete a self-assessment of withdrawal symptoms using the SOWS. This form contains 16 questions that rate the intensity of withdrawal from 0 (“Not at all”) to 4 (“Extremely”). A copy of the SOWS is provided in the Study MOP.

9.3.5.2. Clinical Opioid Withdrawal Scale (COWS)

Study personnel will assess clinical observations indicative of withdrawal using the COWS. This scale consists of 11 common opiate withdrawal signs or symptoms, rated on a numeric scale and based on a timed period of observation of the subject by the rater. A copy of the COWS is provided in the Study MOP.

9.3.6. Urine Toxicology for Other Drugs of Abuse

Urine will be tested for other drugs of abuse (e.g., cocaine, benzodiazepines, barbiturates, amphetamines, phencyclidine and cannabinoids [THC]) and for alcohol using qualitative methods. Positive results will not be confirmed using quantitative methods.

9.3.7. Unscheduled Visits, Medication and Counseling

Temporary adjustments in BPN doses will be allowed using CAM2038 q1w SC booster injections (8 mg) at unscheduled visit(s). A maximum of two SC booster injections will be allowed per week. Subject-requested or physician-directed supplemental visits, phone calls or additional counseling, or other pharmacological interventions, along with the reason(s) for unscheduled visits, booster injections, phone calls or additional counseling or other pharmacological interventions, will be recorded.

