7.1.2. Treatment Phase (Week 1 to Week 48)

7.1.2.1. Day 1 (Week 1) (CAM2038 q1w)

New entrants to BPN Treatment: On Day 1, for subjects who are **not currently receiving SL BPN or buprenorphine/naloxone (SL BPN/BPX)**, treatment will be initiated with CAM2038 q1w in the following manner:

Day 1: On Day 1, subjects will receive the following, while on site:

- A 4 mg SL BPN tablet test dose and observed for at least 1 hour prior to study drug administration.
- Once tolerability is confirmed (i.e., no precipitated withdrawal symptoms), a single CAM2038 q1w (once-weekly) 16 mg injection (0.32 mL of active) will be administered.

Day 2: All subjects will return to the clinic on Day 2 to ensure tolerability.

Day 4: All subjects will return to the clinic. Subjects who return on Day 4 still experiencing withdrawal symptoms should receive a single CAM2038 q1w 8 mg SC injection (0.16 mL of active). A visit window of

±1 day is allowed for the Day 4 visit.

Days 5 to 7: Subjects requiring additional dosage adjustments may return to the clinic on Days 5 to 7 if needed, based on withdrawal symptoms or tolerability. Subjects who require additional increases in dose will receive up to two additional CAM2038 q1w 8 mg SC injections (0.16 mL of active) (i.e., up to a maximum of 40 mg SC injection dose per week).

Subjects Currently on Weekly BPN Treatment: Subjects who are **currently receiving SL BPN/BPX** and are considered a candidate for CAM2038 q1w treatment by the Investigator will be transitioned to CAM2038 q1w in the following manner:

- Subjects will receive a single CAM2038 q1w SC injection that corresponds to their current SL BPN/BPX dose prior to Day 1:
 - ≤ 6 mg SL BPN/BPX: 8 mg (0.16 mL) CAM2038 q1w SC injection
 - 8-10 mg SL BPN/BPX: 16 mg (0.32 mL) CAM2038 q1w SC injection
 - 12-16 mg SL BPN/BPX: 24 mg (0.48 mL) CAM2038 q1w SC injection
 - 18-24 mg SL BPN/BPX: 32 mg (0.64 mL) CAM2038 q1w SC injection

- Subjects may return to the clinic for additional titration with CAM2038 q1w (8 mg SC booster injections), as needed, up to a maximum weekly dose of 40 mg per week.

Subjects should not take their ordinary SL BPN tablet(s) on Day 1 (i.e., the last dose of SL BPN should be taken on the day before dosing with CAM2038 q1w).

Subjects will return to the clinic for weekly visits during which they will receive their CAM2038 q1w SC injection treatments.

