7.1.2.3. Treatment Visits (Weeks 2 to 48)

Subjects will return to clinic for visits based on each subject's dose of CAM2038 (q1w – once weekly or q4w – once monthly).

Subjects receiving **CAM2038 q1w** will return to the clinic weekly to receive their next dose and for safety and other assessments as outlined in [Table 3](#). At the discretion of the Investigator, subjects may receive dose adjustments during the scheduled CAM2038 q1w weekly dose visits (up to a maximum weekly dose of 40 mg per week).

Subjects may return to the clinic for additional titration with CAM2038 q1w (8 mg SC booster injections) as needed (i.e., at unscheduled visits), up to a maximum weekly dose of 40 mg per week.

At any weekly visit, the Investigator may transition subjects from weekly (CAM2038 q1w) to monthly (CAM2038 q4w) clinic visits after, at the minimum, taking the following criteria into consideration on the day of the visit where the transition of dose will occur (ie. Prior to new dose administration):

- Subject is on a stable dose of CAM2038 q1w without any additional fluctuations in dose for 4 weeks
- Subject has minimal subjective and no objective withdrawal symptoms, based on the SOWS and COWS scores (SOWS \leq 7 and COWS \leq 5).
- Subject exhibits diminished desire/need to use, based on VAS scores.

- Subject has diminished use of illicit opioids, according to the Investigator's discretion

Subjects who are eligible for **transitioning from CAM2038 q1w to CAM2038 q4w** will be transitioned in the following manner:

- Subjects will receive a single CAM2038 q4w SC injection, using the following conversion guidelines:
 - 16 mg (0.32 mL) CAM2038 q1w: 64 mg (0.18 mL) CAM2038 q4w
 - 24 mg (0.48 mL) CAM2038 q1w: 96 mg (0.27 mL) CAM2038 q4w
 - 32 mg (0.64 mL) CAM2038 q1w: 128 mg (0.36 mL) CAM2038 q4w

In addition, per Investigator's discretion, subjects may be switched back from monthly CAM2038 q4w visits to CAM2038 q1w weekly visits at any time during the Treatment Phase, if weekly dose visits are deemed to be appropriate based on the Investigator's clinical judgment on subject's level of stability.

Subjects receiving **CAM2038 q4w** will return to the clinic monthly to receive their next dose, and for safety and other assessments outlined in [Table 3](#).

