Subjects may receive temporary dose adjustment while receiving CAM2038 q4w, at the Investigator's discretion, using booster CAM2038 q1w 8 mg SC injections at any time during the study (through unscheduled visits, as needed). At the discretion of the Investigator, subjects may also receive dose adjustments during the scheduled CAM2038 q4w monthly dose visits. The temporary dose adjustments, or booster CAM2038 q1w 8 mg SC injection may be given at a maximum of two boosters per week.

At each visit (weekly or monthly), the following will be assessed:

- Urine samples for opioid toxicology, evaluated using immunoassay (qualitative) with reflex quantitative confirmation methods. Urine will also be tested for other drugs of abuse (e. g., cocaine, benzodiazepines, barbiturates, amphetamines, phencyclidine, and THC) and for alcohol using qualitative methods.
- Self-reported use of all drugs, including illicit or prescription opioids and other prescribed or illicit drugs.
- Measures of withdrawal using the Clinical Opioid Withdrawal Scale (COWS) and the Subjective Opioid Withdrawal Scale (SOWS)
- Measures of craving using Desire to Use and Need to Use visual analog scales (VAS)
- Other safety assessments and measures as outlined in [Table 3](#).

7.1.3. Follow-up Phase (Week 49 to 53):

Following the last Treatment Visit, subjects will be transitioned to standard care (e.g., SL BPN/BPX) at Week 49. Additional assessments will be performed during Week 53 outlined in [Table 3](#).

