8. TREATMENTS

8.1. Treatment Administration

Subjects will receive CAM2038 treatment for up to 12 months (48 weeks) during the study:

- For subjects who are not currently receiving SL BPN or SL BPN/BPX, treatment will be initiated with a single CAM2038 q1w 16 mg SC injection (following a 4 mg SL BPX test dose); additional dose adjustments will be allowed up to maximum weekly dose of 40 mg.
- Subjects who are currently receiving SL BPN/BPX will be transitioned to CAM2038 q1w or q4w SC injections according to their current dose of SL BPN/BPX (Table 2).
- SC injection administration sites: Rotate from left and right side of buttock. Injection with CAM2038 q1w will be rotated in a manner to not re-inject in the same location for at least 8 weeks, (i.e., injection into the same site will only occur after 8 weeks). Injection with CAM2038 q4w will be rotated and the same site will not be utilized for the duration of the study.
- Additionally, a q4w injection dose can be injected into a previously used q1w injection site following the q1w rule: Injection with CAM2038 q1w will be rotated in a manner to not re-inject in the same location for at least 8 weeks, (i.e., injection into the same site will only occur after 8 weeks)

A diagram of potential injection sites will be provided in the Study Manual of Procedures (MOP).

Table 2: Doses of CAM2038 q1w and q4w for Subjects Transitioning from SL BPN/BPX

Weekly SL BPN/BPX Category	Once Weekly CAM2038 q1w SC Injection^a
≤ 6 mg	8 mg (0.16 mL)
8-10 mg	16 mg (0.32 mL)
12-16 mg	24 mg (0.48 mL)
18-24 mg	32 mg (0.64 mL)
Monthly SL BPN Category	Once Monthly CAM2038 q4w SC Injection^b
8-10 mg	64 mg (0.18 mL)
12-16 mg	96 mg (0.27 mL)
18-24 mg	128 mg (0.36 mL)

26-32 mg	160 mg (0.45 mL)
----------	------------------

BPN = buprenorphine; BPX = buprenorphine/naloxone; SC = subcutaneous; SL = sublingual

^a Subjects may return to the clinic for additional dose adjustments with CAM2038 q1w at scheduled visits or 8 mg SC booster injections at unscheduled visits, as needed, up to a maximum weekly dose of 40 mg per week.

^b Subjects needing additional temporary BPN while receiving CAM2038 q4w may receive a maximum of two boosters of CAM2038 q1w 8 mg SC injection per week (i.e., unscheduled visits). Dose adjustments may also be implemented at the discretion of the Investigator at scheduled visits.

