8.4. Selection of Doses

The study will include the proposed range of CAM2038 q1w and q4w doses to be used in clinical practice, based on each subject's individual needs. As in clinical practice, dose adjustments (increases in case of withdrawal effects or cravings or decreases for tolerability reasons) will be allowed during the study. In addition, booster injections of CAM2038 q1w 8 mg will be allowed during the study for those receiving either CAM2038 q1w or CAM2038 q4w (up to a maximum weekly dose of 40 mg per week for subjects receiving CAM2038 q1w, or a maximum of two boosters per week for subjects receiving CAM2038 q4w).

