4.2 STUDY TREATMENTS

Following Screening, qualified patients will be initiated on either CAM2038 q1w or q4w, based on their current treatment status (qualified patients currently on sublingual (SL) BPN or seeking BPN treatment). Qualified patients will be initiated or transitioned to CAM2038 q1w or q4w as follows:

- Initiation of BPN treatment – initiate with CAM2038 q1w
- Currently receiving SL BPN treatments – transfer to corresponding CAM2038 q1w or q4w dose

Patients will be allowed to receive supplemental BPN during the study with booster SC injections of CAM2038 q1w 8 mg up to a maximum dose of 40 mg CAM2038q1w per week. For patients on CAM2038 q4w, a maximum of two booster doses of CAM2038 q1w 8 mg SC injections may be given per week. Dose adjustments (up or down titrations) will also be allowed at scheduled visits.

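### Protocol 9.3.7 caps boosters at two per week without naming a regimen, but the dosing sections and SAP 4.2 limit q1w subjects by a 40 mg weekly total instead

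*Protocol*

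**What the plan says.** Protocol 9.3.7 (Unscheduled Visits, Medication and Counseling) allows temporary dose adjustment with 8 mg CAM2038 q1w boosters at unscheduled visits and then sets the limit: "A maximum of two SC booster injections will be allowed per week". It does not say which regimen this applies to and does not mention a weekly dose ceiling.

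The other places that set a booster limit separate the two regimens.

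**Subjects on q1w: a weekly dose ceiling, no count.**
- Protocol 7.1.2.1, for subjects transferring from sublingual buprenorphine in Week 1: "additional titration with CAM2038 q1w (8 mg SC booster injections), as needed, up to a maximum weekly dose of 40 mg per week".
- Protocol 7.1.2.3, for Weeks 2 to 48: "as needed (i.e., at unscheduled visits), up to a maximum weekly dose of 40 mg per week".
- Protocol 8.1, Table 2 footnote a: "8 mg SC booster injections at unscheduled visits, as needed, up to a maximum weekly dose of 40 mg per week".

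**Subjects on q4w: a count of two per week.**
- Protocol 7.1.2.3, in the paragraph that opens with subjects receiving q4w: "booster CAM2038 q1w 8 mg SC injection may be given at a maximum of two boosters per week".
- Protocol 8.1, Table 2 footnote b: "while receiving CAM2038 q4w may receive a maximum of two boosters of CAM2038 q1w 8 mg SC injection per week".
- SAP 4.2: "For patients on CAM2038 q4w, a maximum of two booster doses of CAM2038 q1w 8 mg SC injections may be given per week". The sentence before it in SAP 4.2 gives the 40 mg weekly maximum.

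Protocol 8.4 puts both limits in one sentence: "up to a maximum weekly dose of 40 mg per week for subjects receiving CAM2038 q1w, or a maximum of two boosters per week", the second part being for q4w subjects.

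**The concern.** Sections 9.3.7, 7.1.2.3 and Table 2 footnote a all govern the same act, an 8 mg booster at an unscheduled visit, but they set different limits for a q1w subject. No rule in the documents says which section prevails.

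A third booster in one week for a subject on 16 mg is permitted by 8.4 and barred by 9.3.7. Protocol 8.4 ties dose increases to withdrawal effects or cravings, so a site working from 9.3.7 would withhold a dose that the dosing sections allow for those symptoms. In the other direction, a site that relied on 9.3.7 alone could give two boosters on top of 32 mg and pass the 40 mg ceiling. Two sites could treat the same subject differently and each cite the protocol. It would also be unclear whether that third booster is a deviation, and SAP 12.0 plans to summarise major deviations in treatment compliance.

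**Working it through.** **Inputs**
- q1w weekly doses: 8, 16, 24 and 32 mg (Protocol 8.2).
- Booster: 8 mg of CAM2038 q1w (Protocol 9.3.7, 8.4).
- q1w ceiling: 40 mg per week (Protocol 7.1.2.1, 7.1.2.3, Table 2 footnote a, 8.4; SAP 4.2).
- 9.3.7 limit: 2 boosters per week.

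**The plan's own 40 mg figure.** Protocol 7.1.2.1 starts new entrants on 16 mg, adds 8 mg on Day 4 if withdrawal symptoms persist, and allows up to two further 8 mg injections on Days 5 to 7: 16 + 8 + 2 × 8 = 40 mg. This matches the maximum stated there. Protocol 5.3 also foresees a single 8 mg booster on top of 32 mg: 32 + 8 = 40 mg.

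**Formulas for a q1w subject on weekly dose d**
- Boosters under 8.4: (40 − d)/8. The weekly total is then 40 mg.
- Weekly total under 9.3.7 read alone: d + 2 × 8.
- Boosters if both limits apply: the smaller of 2 and (40 − d)/8.

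| q1w dose | 8.4: boosters, total | 9.3.7 alone: boosters, total | 9.3.7 alone minus 8.4 | Both limits: boosters, total |
|---|---|---|---|---|
| 8 mg | (40 − 8)/8 = 4, 40 mg | 2, 8 + 16 = 24 mg | −16 mg | 2, 24 mg |
| 16 mg | (40 − 16)/8 = 3, 40 mg | 2, 16 + 16 = 32 mg | −8 mg | 2, 32 mg |
| 24 mg | (40 − 24)/8 = 2, 40 mg | 2, 24 + 16 = 40 mg | 0 | 2, 40 mg |
| 32 mg | (40 − 32)/8 = 1, 40 mg | 2, 32 + 16 = 48 mg | +8 mg | 1, 40 mg |

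Read alone, 9.3.7 departs from 8.4 at three of the four q1w doses. With both limits applied, the departure remains at two of the four, 8 and 16 mg.

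**q4w subjects.** The limit is two boosters per week in 9.3.7, 7.1.2.3, Table 2 footnote b, 8.4 and SAP 4.2. There is no conflict.

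**Week 1 induction.** The Day 4 injection plus two on Days 5 to 7 makes three additions of 8 mg in one week, which would break a two-booster limit if all three count as boosters. Day 4 is a planned visit, so that is arguable, and nothing here depends on it.

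**The case against.** The best defence is that 9.3.7 is a shortened form of the q4w rule. It sits under Efficacy Assessments, much of it concerns what to record about unscheduled contacts, and its talk of temporary adjustment and two boosters per week resembles the q4w paragraph of 7.1.2.3, whereas the q1w text there speaks of titration. The operative dosing sections are explicit. A reader of the whole protocol would also apply the 40 mg ceiling, so nobody on 32 mg should reach 48 mg. What remains, at 8 and 16 mg, errs on the cautious side, arises only when a subject needs a third or fourth booster in one week, and ends at the next weekly visit, when 7.1.2.3 allows the dose to be raised. Protocol 8.2.2 meanwhile allows counselling and other drug treatment, and SAP 11.1.1 summarises the injections actually given, whichever limit a site used.

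Much of this stands. The 48 mg figure needs 9.3.7 to be read alone, the q4w rule is consistent throughout, and the practical effect is small. The q4w-only reading does not hold, though. Section 9.3.7 names no regimen, Protocol 7.1 uses the idea of temporary dose adjustment with boosters for subjects in general, and unscheduled visits are equally the setting of the q1w rule in 7.1.2.3 and Table 2 footnote a. Reading the sections together does not help at 8 and 16 mg, because one section permits what another forbids.

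**Conclusion.** The concern holds: the sentence in 9.3.7 is correct for q4w and wrong as written for q1w. It is 16 mg too strict at q1w 8 mg and 8 mg too strict at 16 mg, agrees at 24 mg, and is 8 mg too loose at 32 mg only if the 40 mg ceiling is overlooked. This takes 8.4 as the intended rule, because 8.4 states both limits by regimen and 7.1.2, Table 2 and SAP 4.2 agree with it. The dosing rule itself is not in question.

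The consequence is minor. Both limits are ceilings and can be met together, so no instruction is impossible to follow. The documents do not say how often a q1w subject on 8 or 16 mg would need more than two boosters in a week, so the number affected cannot be estimated. Sample size and planned analyses are untouched. It should still be corrected, because it is a dosing limit that sites act on.

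**What to change.** Replace the limit in 9.3.7 with the two limits of 8.4, for example: for subjects on CAM2038 q1w, boosters may be given provided the total dose for the week does not exceed 40 mg; for subjects on CAM2038 q4w, no more than two 8 mg boosters may be given in any week. The booster limits for q1w 8, 16, 24 and 32 mg are then 4, 3, 2 and 1 per week, and the q4w limit stays at 2.

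The cost is one sentence in the protocol. The dosing sections, the data collected, the analyses and the SAP stay as they are.
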